8.0 Evaluation During Study

- Follow up visits at MD Anderson every 3-6 months with review of symptoms and physical exam for the first year, then every 6-12 months and thereafter approximately once yearly or at the discretion of the treating physician.
- CBC, platelets, differential, creatinine, bilirubin, and SGPT are recommended twice per year or at the discretion of the treating physician.
- Thyroid function tests are recommended once per year or at the discretion of the treating physician.
- Bone marrow aspiration and biopsy every 3-6 months during the first year, then if needed; cytogenetics once when in complete remission if abnormal prior to therapy.

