4.6 Clinical Studies in Healthy Volunteers

PEG IFN- α 2a was administered by subcutaneous injection to 92 healthy volunteers in a phase I double-blind study. Volunteers received single ascending doses of 45, 135 or 270 μ g of PEG IFN- α 2a or 3 MIU (15 μ g) or 18 MIU (90 μ g) of unmodified interferon- α -2a. Results showed that:

- PEG IFN- α 2a had a more favorable pharmacokinetic profile than interferon- α -2a, with decreased clearance and a serum $t_{1/2}$ approximately 10-fold higher.
- PEG IFN- α 2a had an improved pharmacodynamic profile as compared with interferon- α -2a, as measured by a prolonged elevation of 2'5'-oligoadenylate synthetase following single-dose administration.
- The safety and tolerability profiles of PEG IFN- α 2a are similar to those of interferon- α -2a. Neutropenia was more frequent and more marked in PEG IFN- α 2a treated patients, but neutrophil counts recovered in all cases in less than two weeks following drug administration.

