4.11 Update of study results as of 01/15/2009 and plans

At present the study has accrued 40 patients with PV and 36 patients with ET. Most patients had extensive prior therapies with hydroxurea and anagrelide and all 40 patients with PV had phlebotomies. With a median followup of 24 months on Pegasys therapy, the overall hematologic response rate was 81% with PV (complete

in 78%) and 92% with ET (complete in 86%). These results are the best ever achieved with any form of therapy in PV and ET. In addition, measuring JAK2 V617F mutations, we observed complete molecular responses in 12% of patients and any molecular response in 53% of patients. Side effects were acceptable. At the Pegasys dose of 90 mcg weekly Grade 3 neutropenia was observed in only 8% of patients and other side effects (fatigue, dizziness, depression) in only 4% of patients each. These findings are a true therapeutic breakthrough in the management of PV and ET and have been also reproduced by investigators in France (Kiladjian et.al Blood 112;3065,2008) who reported with Pegasys therapy in 40 patients with PV a CHR in 78%, a complete molecular response in 24%, and a major molecular response in 69%.

Hoffman-LaRoche, the Company, declined to expand the study and provide free drug. Our results suggest this is the best available treatment for these patients. We would like to expand the study and continue therapy with Pegasys commercial preparation. We propose to include up to 100 patients with PV and 100 patients with ET. This will allow a more precise estimate of hematologic and molecular response with long term follow up, a better estimate of long term survival and toxicity profiles, and a treatment of patients on protocol which affords better care by our leukemia experts and allows future analyses of data in a large cohort including an evaluation of prognostic factors that determine molecular response and long term outcome. Our data was presented at ASH 2008 (Quintas-Cardama, Blood 112:653, 2008).

Update September, 2019

Sixteen patients remain on study for a median of 12 years (range 11 - 13). All patients are on a stable dose of pegylated interferon with normal blood counts. None of the patients have experienced drug-related adverse reactions in 9 years. Changes in the protocol reflect standard of care monitoring of patients in long term complete hematologic remission. This study represents the longest follow up of patients with ET or PV treated with pegylated interferon.

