6.2 Dose Escalation and Dose Reduction

Dose Level	Dose of Pegasys in micrograms SQ weekly
+4	450 mcg
+3	360 mcg
+2	270 mcg
+1	180 mcg
0(starting dose)	90 mcg
-1	45 mcg
-2	45 mcg every other week

Any patient who experiences grade 1 or 2 adverse event (see NCI-CTC guidelines, appendix C) should be maintained on the assigned dose if possible. Treatment should be put on hold if a patient experiences any of the following:

- grade 3-4 laboratory abnormalities
- grade 3-4 constitutional toxicity

Dose adjustments may be made at the discretion of the treating physician.

Questionable cases should be resolved by clinical judgment of the investigator.

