9.2 Toxicity

10.0 Criteria for Removal from the Study

Subjects have the right to withdraw from the study at any time for any reason. An excessive rate of withdrawals can render the study uninterpretable; therefore, unnecessary withdrawal of subjects should be avoided. Should a subject decide to withdraw, all efforts will be made to complete and report the observations as thoroughly as possible. Criteria for discontinuation of therapy include:

- Clearly documented progressive disease (increasing requirement for blood transfusion, increasing spleen size, increasing platelet or white blood cell count, increasing frequency of phlebotomies, or frequency of thromboembolic events) or no response (see section 9.1) within 6 months from the start of the therapy on a given dose (i.e. continuously on the same dose level of PEG-IFN α -2a). **Caution:** Patient without response after 3 months on a given dose should have the dose escalated if possible (see section 6.2); if no response when on the escalated dose for 6 months, then therapy should stop.
- Severe toxicities not responding to dose adjustments (see section 6.2)
- Non-compliance to protocol requirements (see section 5.0)

- Development of other conditions for which, in the Investigator's opinion, it is in the subject's best interest to be withdrawn from the study.

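### Is the twice-yearly blood-test schedule in Section 8.0 too sparse for the response and toxicity rules elsewhere in the protocol?

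*Combined protocol and SAP*

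**What the plan says.** Section 8.0 (Evaluation During Study) sets the blood tests in one line: "CBC, platelets, differential, creatinine, bilirubin, and SGPT are recommended twice per year or at the discretion of the treating physician". Two other lines in that section do separate early from later treatment: "Follow up visits at MD Anderson every 3-6 months with review of symptoms and physical exam for the first year", and "Bone marrow aspiration and biopsy every 3-6 months during the first year, then if needed".

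Other sections use blood results:

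- Section 10.0: "Patient without response after 3 months on a given dose should have the dose escalated if possible", and "if no response when on the escalated dose for 6 months, then therapy should stop". Rising platelet or white cell counts also count there as progression.
- Section 6.2: "Treatment should be put on hold if a patient experiences any of the following". The list is grade 3-4 laboratory abnormalities and grade 3-4 constitutional toxicity.
- Section 9.1: CR in ET needs a platelet count and CR in PV needs a haemoglobin value.
- Section 11.1: the study stops for severe toxicity at limits set at 15, 30 and 45 patients.

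The September 2019 update in Section 4.11 gives the reason for the monitoring text: "Changes in the protocol reflect standard of care monitoring of patients in long term complete hematologic remission".

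**The concern.** Taken alone, the laboratory line in Section 8.0 covers every patient from the first injection. A patient monitored only to that line could reach the 3-month step with no count since baseline, although that step often turns on a platelet or haemoglobin value. Brief laboratory toxicity could come and go between two tests six months apart. That would weaken the hold rule in Section 6.2, the toxicity objective in Section 2.2 and the stopping limits in Section 11.1. Section 11.2 still allows up to 100 patients per disease, so on its face new patients could start under this schedule.

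**Working it through.** The plan states no operating characteristic that depends on the laboratory schedule, so there is no figure to reproduce. The check has four parts.

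**1. Timing.** Two tests a year is 12/2 = 6 months, or 52/2 = 26 weeks, between tests. On an even grid from the start of treatment, counts fall at months 6 and 12.

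| Decision (Section 10.0) | Month | Scheduled count available |
|---|---|---|
| Escalation after 3 months on a dose | 3 | none since baseline |
| No response after 6 months on the first dose | 6 | month 6 |
| 6 months on a dose escalated at month 3 | 3 + 6 = 9 | month 6, by then 3 months old |

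The mismatch is real at months 3 and 9 but not at month 6. It is also partial. In Section 9.1, PR in PV rests on phlebotomy rate or spleen size, and PR in ET can be met through fewer thromboembolic events. Neither route needs a blood test.

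**2. Detection of a short episode.** Assume one episode at a random time and scheduled tests only. Then the probability of detection = duration / 26 weeks:

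- 2 weeks: 2/26 = 8%
- 4 weeks: 4/26 = 15%
- 8 weeks: 8/26 = 31%

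A true 20% laboratory toxicity rate would then show as 0.20 × 0.077 = 1.5%, 0.20 × 0.154 = 3% or 0.20 × 0.308 = 6%. The inputs fit this trial poorly. The 2-week figure comes from Section 4.6, where "neutrophil counts recovered in all cases in less than two weeks following drug administration" describes single doses in healthy volunteers, while dosing here is weekly and continuing. The 4- and 8-week durations are assumptions. Tests ordered at discretion or because of symptoms are left out.

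**3. The toxicity stopping rule.** The limits are 7/15 = 47%, 11/30 = 37% and 15/45 = 33%. A true 20% rate lies below all three even with every event detected, so setting 1.5% to 6% against them does not show a missed stop. Exact sequential binomial calculation gives these probabilities of stopping, with assumed shares of events detected:

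| True rate | Share detected | Stop at or above the limit | Stop only above the limit |
|---|---|---|---|
| 20% | 100% | 0.048 | 0.018 |
| 40% | 100% | 0.88 | 0.80 |
| 40% | 75% | 0.43 | 0.29 |
| 40% | 50% | 0.05 | 0.02 |

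Poor detection would therefore matter if it applied during the looks. But the last look is at 45 patients, and Section 4.11 reports 40 + 36 = 76 accrued by January 2009. Monitoring changes explained in a 2019 update cannot affect looks already passed. The rule also counts severe toxicity of any kind, not only laboratory events.

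**4. Who is on the schedule.** Section 4.11 reports 16 patients in September 2019, 11 to 13 years on study. Counting back, 2019 − 13 = 2006 and 2019 − 11 = 2008, so all entered around 2006 to 2008. It describes stable doses, normal counts and no drug-related adverse reactions in 9 years. None of them is near a first 3-month decision.

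**The case for a change.** The strongest case for a change rests on the operative text. Section 8.0 keeps a first-year tier for visits and marrow, so it still speaks to newly treated patients, yet it gives them no early blood-test schedule. The discretion clause permits extra tests but requires none, and Section 8.1 itself expects that local doctors will sometimes omit tests. Section 11.2 has not been withdrawn, and nothing in the text closes accrual. Laboratory toxicity does occur: Section 4.11 reports grade 3 neutropenia in 8% of patients at 90 mcg.

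The textual part stands. Section 8.0 does not repeat the scope given in Section 4.11, and no count is guaranteed at month 3 or month 9. The step from there to harm does not stand. The entry allowance in Section 11.2 dates from January 2009, and no patient is shown starting treatment under the present schedule. The 8% figure shows that laboratory toxicity was being picked up during the accrual years. The documents do not say which schedule applied then, so under-counting is not established. Coarser timing of response costs no planned result, because time to response is neither an objective nor a listed analysis.

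**Conclusion.** No change to the plan is called for. Section 8.0 carries a late-phase maintenance schedule beside rules written for early treatment, and Section 4.11 tells the reader which patients that schedule was written for. An analyst or treating physician can fill the gap sensibly, and the discretion clause already allows tests when a decision needs them. Confining the twice-yearly line to long-term patients would leave the 16 known patients exactly as they are and would alter no response rate, toxicity estimate or stopping decision.

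This rests on two readings of the documents: that the 16 patients in the 2019 update are the ones now monitored under Section 8.0, and that nobody is starting treatment or returning to the escalation path. The documents support the first and show nothing against the second, though they do not state that accrual is closed. If a new patient were to enter under this text, Sections 6.2, 8.0 and 10.0 would first have to be reconciled, with the frequency of testing left to the investigators.

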8.1 Monitoring of Patients on Study

Patient will be given instructions and the M.D. Anderson contact name (principal investigator/MD Anderson Leukemia staff treating physician), phone, and fax numbers. The patient's local doctor will be identified, contacted, and the protocol details discussed.

All therapy will be given under the care of the patient's local doctor and MD Anderson Leukemia staff treating physician. The patient's local doctor should contact the MD Anderson Leukemia staff treating physician before any dose modifications are considered, and the modifications should be initiated only by the MD Anderson Leukemia staff treating physician or principal investigator, and complications will be dictated at each follow-up visit.

From past experience, it is recognized that treatment provided in collaboration with patient's local doctor outside MD Anderson may occasionally result in some difficulties such as 1) not performing tests as required, 2) not sending results of tests or updates of patient courses, 3) and not informing on toxicities and hospitalizations. This type of therapy is already broadly practiced in the community. Therefore: 1) we will discuss with the patient's local doctor about the protocol and doses, 2) we will make significant efforts (contact at least twice and document) to retrieve the information (tests, toxicities, hospitalizations), and 3) we will document all the information on follow-up visits. Since information may still be missing in one or more components in some patients (e.g. missing CBC or SMA-7, missing drug administration record), these types of difficulties will be collected and documented in the patient's medical record. This will reflect the oncology community practice of the program.

9.0 Criteria for Response and Toxicity

9.1 Criteria for Response

9.1.1 ET

CR = Reduction of PLT to $<440 \times 10^9/l$ and disappearance of thromboembolic events, without the use of anagrelide or hydroxyurea

PR = Reduction of PLT by 50% but still $>440 \times 10^9/l$ or reduction of thromboembolic events by 50%, without the use of anagrelide or hydroxyurea

9.1.2 PV

CR = Normalization of Hb ($< 15.0 \text{ g/dl}$), no phlebotomies needed, and disappearance of splenomegaly by palpation, without the use of anagrelide or hydroxyurea

PR = A 50% reduction in phlebotomies rate or splenomegaly reduced by 50% by palpation, without the use of anagrelide or hydroxyurea

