5.0 Patient Eligibility Criteria

5.1 Inclusion Criteria

- Following diagnoses:
 - ET: Patients with PLT $> 600 \times 10^9/l$ documented in the past 12 months; hyperplasia of marrow megakaryocytes in the absence of identifiable cause of thrombocytosis and in the absence of Ph chromosome. Patients with ET and lower PLT will be eligible if attributable to prior ET therapy.
 - PV: Patients should have Hb $\geq 15\text{g/dl}$ (except if patient is having phlebotomies done or is taking hydroxyurea) and documented past diagnosis
- Performance status ≤ 2 (ECOG scale; see Appendix A).
- Age greater than 18 years since disease is extremely rare in younger age group.
- Adequate liver function: total bilirubin of $\leq 2.0\text{ mg/dl}$ (except for patients with Gilbert's Syndrome) and AST (SGOT) or ALT (SGPT) $< 3 \times \text{ULN}$ (or $< 5 \times \text{ULN}$ if considered due to tumor), and renal function (serum creatinine $\leq 2.0\text{ mg/dl}$)
- Signed informed consent indicating that patients are aware of the investigational nature of this study in keeping with the policies of the M.D. Anderson Cancer Center. The only acceptable consent form is the one approved by the M.D. Anderson Cancer Center IRB.
- Willingness and ability to comply with the requirements of the protocol for the duration of the study.
- Patients must have been off chemotherapy for 1 week prior to beginning Pegasys and have recovered from the toxic effects of that therapy. Patients may have received hydroxyurea or anagrelide immediately before study entry, and may continue into therapy if treating physician determines that this is in the best interest of the patient.

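### In ET patients with baseline platelets above 880 whose thromboembolic events are not halved, a platelet fall to below 440 scores as no response, while a fall of at least 50% that stops above 440 scores as PR

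*Combined protocol and SAP*

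**What the plan says.** Section 9.1.1 gives two response classes for ET.

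- **CR:** "CR = Reduction of PLT to" below 440 × 10^9/l, joined to "disappearance of thromboembolic events, without the use of anagrelide or hydroxyurea". Both parts are required.
- **PR:** "PR = Reduction of PLT by 50% but still" above 440 × 10^9/l, "or reduction of thromboembolic events by 50%, without the use of anagrelide or hydroxyurea". Either limb is enough. The platelet limb has no event condition, and the event limb has no platelet condition.

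Section 5.1 admits ET patients with a platelet count above 600 in the preceding 12 months. It adds: "Patients with ET and lower PLT will be eligible if attributable to prior ET therapy".

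Section 10.0 makes the classes operational. One ground for discontinuation is "no response (see section 9.1) within 6 months from the start of the therapy on a given dose". The same bullet separately counts a rising frequency of thromboembolic events as progressive disease. No order of precedence between the two is given.

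Section 11.1 sets a 35% response rate per disease as the efficacy criterion and does not say whether that means CR alone or CR plus PR. Section 4.11 reports, for 36 ET patients at the 2009 update, 92% overall response and 86% complete response.

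**The concern.** The lower limit of 440 in the PR platelet limb appears intended to mean short of CR. CR has two parts, however, and the limit negates only the platelet part. A patient who meets the platelet part and fails the event part is not CR. That patient is not platelet PR either, because the count is below the limit. Unless events have fallen by half, no class is left except no response. Another patient with the same baseline and the same events, but a shallower platelet fall of at least 50% that stays above 440, is PR.

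CR, PR and no response are then not ordered by platelet benefit. Response is the efficacy measure for the primary objective, and Section 11.2 justifies the expansion to 100 ET patients partly by more precise response data. A rule that scores the deeper fall as worse works against that purpose. It also supplies the no-response label that Section 10.0 relies on.

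**Working it through.** No sample size, power or alpha figure depends on this point, so there is none to reproduce. The check applies the rule literally and then bounds its effect on the 2009 result.

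**Rule as coded** (Section 9.1.1; no anagrelide or hydroxyurea assumed throughout)

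- CR: platelets < 440 and no event on treatment.
- PR: (fall ≥ 50% and platelets > 440) or (events reduced by ≥ 50%).
- Otherwise: no response (NR).

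Assumptions: the fall is measured from the pre-treatment count, and a first event on treatment (0 → 1) is not a reduction. Section 9.1.1 specifies neither the reference count nor the period over which events are compared.

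**Where the platelet limb can be met.** A fall of at least 50% means on-treatment count ≤ baseline/2. Together with a count above 440 this needs baseline/2 > 440, so baseline > 2 × 440 = 880.

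**Cases.** Fall = (baseline − on-treatment count)/baseline. The last column uses platelet PR = fall ≥ 50%, CR not met.

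| Baseline | On treatment | Fall | Events before → on | As written | Corrected |
|---|---|---|---|---|---|
| 1200 | 600 | 50% | 1 → 1 | PR | PR |
| 1200 | 430 | 64% | 1 → 1 | **NR** | PR |
| 1000 | 500 | 50% | 0 → 1 | PR | PR |
| 1000 | 450 | 55% | 0 → 1 | PR | PR |
| 1000 | 400 | 60% | 0 → 1 | **NR** | PR |
| 1000 | 450 | 55% | 4 → 3 | PR | PR |
| 1000 | 400 | 60% | 4 → 3 | **NR** | PR |
| 1000 | 400 | 60% | 2 → 1 | PR (event limb) | PR |
| 1000 | 700 | 30% | 0 → 1 | NR | NR |
| 880 | 445 | 49% | 1 → 1 | NR | NR |
| 880 | 400 | 55% | 1 → 1 | NR | PR |
| 600 | 400 | 33% | 0 → 1 | NR | NR |

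The bold rows are the reversal: baseline and events match the PR row or rows above, the platelet fall is deeper, and the class is worse. The 2 → 1 row shows that halved events remove it. The 880 rows show that at that baseline the patient is NR on both sides of 440, so nothing is reversed.

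**Size on the 2009 figures** (Section 4.11, assuming all 36 ET patients were evaluable)

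- 92% overall: 33/36 = 91.7%. The neighbouring counts do not fit (32/36 = 88.9%, 34/36 = 94.4%).
- 86% complete: 31/36 = 86.1%. The neighbouring counts do not fit (30/36 = 83.3%, 32/36 = 88.9%).
- Non-responders: 36 − 33 = 3. At most these 3 could be reclassified, so overall response lies between 33/36 (91.7%) and 36/36 (100%).
- CR stays at 31/36, because the CR definition is untouched.
- Both 86% and 92% are far above 35%, so the criterion in Section 11.1 is met whether response means CR or CR plus PR.

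**The case against.** The strongest reply is that the case is rare and any sensible assessor would read PR as anything short of CR. The rarity stands: at most 3 of the 36 ET patients in 2009 could be involved. The protocol does not say how borderline patients were classed. If assessors already read it that way, the re-tabulation will show no change. The text still says otherwise, and no other section repairs it.

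One could also argue that an on-treatment event ought to count as failure whatever the platelet count. The rule does not do that: with the same event, a count of 500 from a baseline of 1000 is PR.

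Section 10.0 covers part of the ground. A patient going from no events to one may meet its progressive-disease clause at either platelet count. Patients with unchanged events (1 → 1), or a fall of less than half (4 → 3), do not have a rising frequency, so for them the 9.1 label matters.

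Some stronger readings are tempting but not supported:

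- A reader might infer that every patient below 440 with an event is a non-responder, and that the same patient above 440 is always PR. Neither half holds. Halved events give PR at any count, and PR above 440 also needs a 50% fall, hence a baseline above 880.
- A reader might take the background thrombosis rates in Section 3.1 (7% to 31% per patient-year in ET) or the hydroxyurea-arm figure in 3.1.1 (3.6% over a median of 27 months) as the share of patients affected. Those rates count anyone with an event, are not trial data, and are not restricted to baselines above 880 or to events not halved.
- A reader might call the empty platelet-PR band at baselines of 880 or less a misclassification. It follows from the thresholds: from a baseline below 880, a 50% fall already meets the platelet part of CR, so an event-free patient is CR.

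**Conclusion.** The point holds in a narrow form. For ET patients with a baseline above 880 whose thromboembolic events are new or fall by less than half, Section 9.1.1 as written ranks a fall to below 440 beneath a fall of at least 50% that stops above 440. The cause is a PR limit that negates only half of a two-part CR definition.

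The effect is confined to ET overall response: at most 3 of 36 patients on the 2009 figures, if all were evaluable. That bound does not extend to patients enrolled after the update, for whom the documents give no response data. The share of ET patients with a baseline above 880 is not given either.

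The documents do not support reading this as a threat to the efficacy conclusion. Nor do they show that anyone was wrongly taken off treatment: the 2019 update describes 16 remaining patients across both diseases, all with normal counts, and does not say why others left. What can be said is that Sections 9.1.1 and 10.0 must be reconciled. No view is taken here on which clinical rule is right. The point is worth correcting but not critical.

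**What to change.** In Section 9.1.1, replace the platelet limb of ET partial response with: platelets reduced by at least 50% from baseline, CR not met. Delete the requirement that the count remain above 440 and leave the event limb and the CR definition as they are.

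Do not add a count below 440 as a route to PR in its own right. Section 5.1 admits patients whose count is already low from earlier therapy, so a patient entering at 450 and reaching 430 with a new event would become a partial responder on a trivial fall. Under the proposed wording, 600 to 400 with an event stays no response, because the fall is only 33%.

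Re-tabulate ET overall response once for all treated ET patients and report both versions side by side. The correction can only move patients upward, including some with baselines of 880 or less (880 to 400 with an unchanged event, for example), and it comes after results were presented. The as-written figure should therefore stay visible.

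State in the same amendment how the 9.1.1 classes and the Section 10.0 grounds for stopping relate, since a change to one changes the reach of the other.

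The cost is one sentence in 9.1.1, a reconciling statement in Section 10.0, and one re-run of the response table on platelet counts and events already collected. The overall ET rate may differ slightly from the one already presented.

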7.0 Pretreatment evaluation

The pre-treatment evaluation will be aimed at confirming/establishing the diagnosis. The evaluation will consist of a through assessment of the following tests: and will be done within a month of enrollment in the study (unless noted otherwise):

- A complete primary evaluation with physical examination
- CBC, platelet counts, differential
- Serum creatinine, bilirubin, SGPT
- Pregnancy test (if of child bearing potential)
- Bone marrow aspiration and biopsy; cytogenetic studies; if not done in the last 3-6 months

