11.0 Statistical Considerations

11.1 This is a phase II trial of PEG IFN-a2a (Pegasys®) as a treatment for ET and PV. In each disease, a response rate of 35% or more would be accepted as evidence for a good efficacy to be further pursued in this disease subsets in larger randomized or combination studies. Therefore, in each disease category, the study will stop if response is 07, < 1/11, <2/15. Otherwise it will accrue 80 patients to better define the response and toxicity profiles. Also, in the total study group, a severe toxicity rate of <20% is allowed. Therefore, the study will also stop if severe toxicity is observed in >7/15, 11/30, 15/45.

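### Section 9.1.2 accepts one unconfirmed 50% fall in the palpated spleen as a PV partial response, so palpation error can turn some patients with a barely palpable spleen into responders

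*Combined protocol and SAP*

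**What the plan says.** Section 9.1.2 gives the PV partial response in one line: "PR = A 50% reduction in phlebotomies rate or splenomegaly reduced by 50% by palpation", on condition that neither anagrelide nor hydroxyurea is used. The two arms are alternatives. The drug condition is the only further requirement; there is no baseline size, unit, duration or confirmation.

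Complete response also uses palpation ("no phlebotomies needed, and disappearance of splenomegaly by palpation"), but only jointly with a normal haemoglobin.

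Nothing elsewhere supplies the missing conditions:

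- Section 5.1 admits PV patients on haemoglobin ("except if patient is having phlebotomies done or is taking hydroxyurea) and documented past diagnosis") and sets no spleen criterion.
- Section 7.0 asks for "A complete primary evaluation with physical examination", without imaging or an instruction to record spleen length.
- Section 8.0 plans "Follow up visits at MD Anderson every 3-6 months with review of symptoms and physical exam for the first year". That is about two to four examinations in year 1, none of them tied to confirming a response.

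Response is then used in three places. Section 11.1 states that "In each disease, a response rate of 35% or more would be accepted as evidence for a good efficacy" and sets early stopping boundaries on response, without limiting it to complete response. Section 10.0 refers to section 9.1 when it defines non-response. Section 4.11 reports an overall PV rate that includes partial responses.

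**The concern.** A percentage threshold on a small, coarsely graded measurement can be crossed by one step of reading error. A spleen felt at 2 cm and later at 1 cm, or at 1 cm and later not felt, has met the rule although nothing need have changed. The plan does not say which examination counts, so if any visit may count, each one is a further chance to cross.

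A response created this way enters the PV partial and overall response rates. Had the drug been inactive, it would also have made the early stopping rule less likely to stop. Section 11.2 names more precise response data as an aim of the expansion, and an unconfirmed palpation threshold works against that aim.

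**Working it through.** The plan gives no error rate for the spleen criterion and no operating characteristics for its stopping rule, so there is no figure to reproduce first.

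**Inputs.** From the documents: the 50% rule (9.1.2), two to four examinations in year 1 (8.0), the 35% target and the boundaries (11.1), and PV overall 81%, complete 78%, 40 patients (4.11). Assumed, because the documents are silent: palpation SD of 0.5, 1.0 or 1.5 cm per examination, errors independent between visits, readings in whole centimetres, and true spleen unchanged.

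**Model.** Reading = max(0, round(true size + SD × z)), with z standard normal. Let p_k be the probability of reading k and F its cumulative sum. Patients with a palpable baseline have weights w_k = p_k / (1 − p_0). Given baseline reading k, one follow-up qualifies with probability q_k = F(⌊k/2⌋).

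- One examination: Σ w_k q_k.
- Any of n examinations: Σ w_k [1 − (1 − q_k)^n].
- Two consecutive out of four: Σ w_k {1 − [(1 − q_k)^4 + 4q_k(1 − q_k)^3 + 3q_k²(1 − q_k)²]}.

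**Worked case: true 2 cm, SD 1.0.** Readings of 0, 1, 2, 3, 4, 5 and 6 cm have probabilities 0.0668, 0.2417, 0.3829, 0.2417, 0.0606, 0.0060 and 0.0002.

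- Baseline 1 needs a follow-up of 0: 0.2417 × 0.0668 = 0.016.
- Baseline 2 or 3 needs at most 1: 0.6247 × 0.3085 = 0.193.
- Baseline 4 or 5 needs at most 2: 0.0666 × 0.6915 = 0.046.
- Baseline 6 adds 0.0002.

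The sum is 0.255, and 0.255 / 0.9332 = 27%.

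**False partial response, no true change (SD 0.5 / 1.0 / 1.5 cm):**

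| True spleen | One examination | Any of two | Any of four | Two consecutive of four |
|---|---|---|---|---|
| 2 cm | 13 / 27 / 37% | 25 / 45 / 58% | 42 / 65 / 78% | 6 / 21 / 32% |
| 3 cm | 3 / 14 / 24% | 5 / 25 / 40% | 8 / 39 / 60% | 1 / 8 / 17% |
| 8 cm | 0 / 0.1 / 1.4% | 0 / 0.1 / 2.7% | 0 / 0.2 / 5.1% | 0 / 0 / 0.2% |

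**Effect on the PV rate.** Added points = share of patients with a small spleen × false-response chance. The share is unknown; take 20 to 40% as an illustration. Low end: 20% × 3% = 0.6 points. High end, reading the rule as any of four visits: 40% × 65% = 26 points.

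**Effect on early stopping.** Section 11.1 is read as 0/7, at most 1/11, at most 2/15. The exact probability of stopping is above 99% at an apparent response rate of 0.6%, 97% at 5%, 66% at 15% and 30% at 25%. If the printed less-than signs are taken strictly, the last three are 87%, 43% and 16%.

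**What was observed.** 81% − 78% = 3 points for all partial responses from both arms. On 40 patients that is 0.03 × 40 = 1.2. The percentages also fit 30/37 and 29/37, a difference of one patient.

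**The case against.** The strongest reply is that little of this harm could have materialised. By January 2009, 40 PV patients had been accrued, so the looks at 7, 11 and 15 were past. Section 11.2 turned the study into an estimation exercise and states no new futility look. By September 2019 sixteen patients remained. Even if every partial response reported in 2009 were false, 78% complete response is more than twice the 35% target. This stands, and it limits the point.

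A reader might infer that palpation error inflated the reported PV efficacy or carried the drug past its futility rule. The documents do not support either reading. A misread spleen cannot create a complete response alone, because haemoglobin and phlebotomy must also qualify, and partial responses add only about 3 points.

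The inputs can also be challenged. SD, spleen sizes and the small-spleen share are all assumed. Errors correlated across visits, for instance with the same examiner, would lower the figures. Any-of-four is the most permissive reading; section 10.0's six-month window covers only one or two visits. The phlebotomy arm has random variation of its own, so the true no-effect rate without the spleen arm need not be zero. These objections stand against any single headline number. They do not remove the mechanism, which follows from the wording of 9.1.2.

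Finally, examinations are repeated under 8.0. True, but none is required to confirm a response.

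**Conclusion.** The point holds as a weakness in the definition of PV partial response. Reading error of one centimetre can make some patients with a barely palpable spleen into responders, and nothing in the plan prevents it. For spleens of 2 to 3 cm the chance is appreciable at every SD assumed except the smallest, where a 3 cm spleen gives only 3% at one visit. For large spleens it is negligible.

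The affected quantities are the PV partial and overall response rates, and the way the rule would have behaved had activity been low. The size in points cannot be fixed from the documents. The complete-response conclusion is not affected. This is an inexpensive improvement to the endpoint and does not invalidate the trial.

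**What to change.** For the response endpoint in 9.1.2, count the spleen arm of PV partial response only when the 50% reduction is found at two consecutive scheduled examinations under 8.0. For a 2 cm spleen at SD 1.0 over four visits this lowers the false-response chance from 65% to 21%. Some risk remains because both follow-up readings are compared with the same single baseline reading. Therefore also report the PV partial and overall response rates with and without spleen-only responses, by recorded baseline spleen size, as far as the records allow.

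A fixed minimum such as 5 cm is not recommended. It has no basis in the documents and, applied to one baseline reading, it selects over-readings: at SD 1.0 about 7% of true 3 cm spleens read 5 cm or more, and 28% of those would still show a confirmed false response over four visits.

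The cost is one sentence in 9.1.2 and one added tabulation, using visits already planned. A spleen response is dated one visit later, and the PV partial-response rate may be slightly lower. Because section 10.0 refers to response under 9.1, the sponsor must reconcile the two sections; no rule for stopping or changing treatment is proposed here.
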